16.1.4.3. Time to All-cause Discontinuation

Time To all-cause discontinuation will be analyzed using a time-to-event analysis. KM results will be displayed for the 25%, 50% and 75% quartiles, including its 95% confidence interval using the product limit method. The KM figure will be produced to support the analysis. Time to all-cause discontinuation will be presented for all subjects up to Week 28 overall, by country, Sex, Age and Mood Stabilizer separately, and repeated for all Japanese subjects up to Week 52 overall, by Sex, Age, Mood Stabilizer, Most Recent or Current Episode, Bipolar I Subtype and Psychotic Features separately as well.

Time to all-cause discontinuation for subjects with more than 28 Weeks of treatment duration after clinical stability will also be analyzed using a time-to-event analysis and presented for all Japanese subjects up to Week 52.

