4.4 Discontinuation of patients from the study

4.4.1 Criteria of discontinuation

Patients may be discontinued from the study treatment and assessments at any time for any of the following reasons:

- Adverse event
- Lack of efficacy
- Pregnancy
- Withdrawal by patient
- Noncompliance
- Protocol violation
- Lost to follow-up
- Other

The investigator should terminate the study treatment if a female patient becomes pregnant (see Section 7.2, Page 64) or if any adverse events or lack of efficacy results in psychotic hospitalization.

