4.4.2 Procedures for discontinuation

When a patient discontinues before study completion, the investigator should perform all applicable activities scheduled at the time of discontinuation and record the primary reason in the electronic case report form (eCRF). The investigator will access the IWRS and update the patient final status. The date of discontinuation is defined as the date of final administration of the study drug. The study drug unused or partially

used should be returned by the patient.

If a patient discontinues the study treatment because of any AEs, the patient should be monitored until resolution or stabilization of the AE, and the investigator should perform the best possible observation, tests and evaluation as well as give appropriate treatment and take all possible measures for the safety of the patient. Any AEs that are present at the time of discontinuation/withdrawal should be followed in accordance with the safety requirements outlined in Section 6.3.1.4 (see Page 58).

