14.3. DERIVATIONS

Cumulative dose (mg) = Sum of all the doses the subject is expected to take during the study.

Duration of exposure (days) = (date of last study medication administration – date of first study medication administration) + 1.

Interruptions, compliance, and dose changes are not taken into account for duration of exposure.

Mean daily dose (mg/day) of study medication = Cumulative dose (mg)/Duration of exposure (days).

The modal daily dose (mg/day) is defined as the daily dose that is taken for the most time for each study phase, in terms of number of days among all doses taken. If there are ties, therefore more than one modal daily dose for a subject, the last modal dose administered will be used in the summaries.

The modal daily dose (mg/day) between visits is calculated similarly to the modal daily dose for overall. Therefore, the dose that is taken for the most time from the visit date to the day prior to the next visit date.

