16.1.1.5. Hamilton Rating Scale for Anxiety (HAM-A)

The HAM-A is a 14-item rating scale developed to quantify the severity of anxiety symptomatology, measured at Screening, Baseline, Weeks 4, 12, 20 and 28 (for subject outside Japan) and Weeks 4, 12, 20, 28, 36, 44 and 52 for subject in Japan.

The 14 items are: anxious mood, tension, fears, insomnia, intellectual, depressed mood, somatic (muscular), somatic (sensory), cardiovascular symptoms, respiratory symptoms, gastrointestinal symptoms, genitourinary symptoms, autonomic symptoms, and behavior at interview. Each of the 14 items is rated on a 5-point scale, ranging from 0 (not present) to 4 (severe/disabling).

The HAM-A total score is the sum of the 14 individual items and ranges from 0 to 56. Higher scores are associated with a greater degree of anxiety. If one or more items are missing at a visit, the total score will be set to missing.

16.1.1.6. Time to recurrence/relapse of any mood event from clinical stability of bipolar disorder

Clinical stability is defined as a total score of ≤ 12 on the YMRS and the MADRS over at least 12 weeks, with the allowance of 2 excursions (the YMRS and/or MSDRS total scores up to 13 or 14, respectively) except during the last 4 weeks before achieving clinical stability.

Duration of stabilization period is defined as the time period during which subjects achieve and maintain

Document:	K:\DSP\SM-13496\RVA97109\Biostatistics\Documentation\SAP		
Author:	[REDACTED]	Version Number:	1.0
		Version Date:	20MAR2018

Template No: CS_TP_BS016 – Revision 3
Effective Date: 01May2012

Reference: CS_WI_BS005

Copyright © 2012 [REDACTED] All rights reserved.
The contents of this document are confidential and proprietary to [REDACTED]. Unauthorized use, disclosure or reproduction is strictly prohibited.

clinical stability during the study. If a subject experiences > 2 excursions within the projected stabilization period, the stabilization "clock" must be restarted and counting of weeks of the stabilization period will start again. The duration of the stabilization period will be calculated as: ((date of stabilization – date of first dose of study medication) +1).

Recurrence/relapse of any mood event is defined as any of the following criteria:

1. Fulfilled DSM-IV-TR criteria for major depressive, manic, mixed, hypomanic episode

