2. Required treatment intervention for major depressive, manic, mixed or hypomanic episode symptoms with any antipsychotic (other than study medication), antidepressant, mood stabilizer (other than lithium or VPA), anxiolytic or benzodiazepine (beyond dosage allowed for anxiety, agitation or insomnia in the protocol)
3. Psychiatric hospitalization for any bipolar mood episode
4. YMRS or MADRS total score ≥ 18 or at least one of the CGI-BP-S (overall, depression, mania) scores ≥ 4 at two consecutive assessments no more than 10 days apart
5. Discontinuation from the study because of a mood episode (as determined by the Investigator)

Time to recurrence of any mood event from clinical stability is defined as ((date of first recurrence of any mood event – clinical stability date) + 1). Time to recurrence will be censored at the time of study completion or early termination, defined as ((date of study completion or discontinuation – clinical stability date) + 1), for subjects who discontinue or complete the study without experiencing any recurrence of mood event.

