16.1.1.7. Time to All-cause Discontinuation

The time to all-cause discontinuation is defined as ((date of discontinuation – date of first dose of study medication) + 1). When a subject completes the study, the time to event is censored at the time of study completion.

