Time to recurrence/relapse of any mood event from clinical stability of bipolar I disorder for subjects with more than 28 Weeks of treatment duration after clinical stability will also be analyzed using a time-to-event analysis and will be presented for all Japanese subjects up to Week 52.

The frequency and percentages of subjects with clinical stability as well as subject who experience a recurrence/relapse of any mood event from clinical stability will be summarized as well as the duration of stabilization which will be summarized descriptively. Summaries will be based on the safety population, by

Document:	K:\DSP\SM-13496\RVA97109\Biostatistics\Documentation\SAP		
Author:	[REDACTED]	Version Number:	1.0
		Version Date:	20MAR2018

Template No: CS_TP_BS016 – Revision 3
Effective Date: 01May2012

Reference: CS_WI_BS005

Copyright © 2012 [REDACTED] All rights reserved. [REDACTED]
The contents of this document are confidential and proprietary to [REDACTED]. Unauthorized use, disclosure or reproduction is strictly prohibited.

treatment group for all subjects up to Week 28 overall and by country separately, and will be repeated for all Japanese subjects up to Week 52 separately as well.

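### Two Japan-only Kaplan-Meier analyses use an undefined subset (over 28 weeks on treatment after stability); if this means achieved treatment, the discontinuation curve selects on its own outcome and some early relapses drop out

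*SAP*

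**What the plan says.** SAP 16.1.4.2 and 16.1.4.3 first plan unrestricted Kaplan-Meier analyses of relapse and of all-cause discontinuation, including Japanese subjects to Week 52. Each section then adds a second, restricted analysis for Japanese subjects:

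- Discontinuation (16.1.4.3): "Time to all-cause discontinuation for subjects with more than 28 Weeks of treatment duration after clinical stability will also be analyzed".
- Relapse (16.1.4.2): "Time to recurrence/relapse of any mood event from clinical stability of bipolar I disorder for subjects with more than 28 Weeks of treatment duration", again counted after clinical stability.

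The definitions that bear on the restriction are:

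- SAP 16.1.1.7, discontinuation clock: "The time to all-cause discontinuation is defined as ((date of discontinuation – date of first dose of study medication) + 1".
- Protocol 4.4.2, discontinuation date: "The date of discontinuation is defined as the date of final administration of the study drug".
- SAP 14.3, exposure: "Duration of exposure (days) = (date of last study medication administration – date of first study medication administration) + 1".
- SAP 16.1.1.6, time to stability: "The duration of the stabilization period will be calculated as: ((date of stabilization – date of first dose of study medication) +1". Stability itself needs low scores over at least 12 weeks, and relapse time is counted from the stability date.
- SAP 16.1.1.6, fifth relapse criterion: "Discontinuation from the study because of a mood episode (as determined by the Investigator".
- Protocol 4.4.1 tells the investigator to end study treatment "if any adverse events or lack of efficacy results in psychotic hospitalization".

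SAP 3.1 speaks of treatment duration as the planned 28 or 52 weeks. No section gives a formula for treatment duration after stability. Protocol 9.5.2 has no such restricted analysis, and SAP 3.6 does not list one among the changes from the protocol.

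**The concern.** A subset defined by how long subjects stayed on treatment is not a baseline subgroup. If the phrase means treatment actually received, a subject enters the discontinuation analysis only by not discontinuing for 28 weeks after stability. The early part of the curve then carries no information, and the later part describes only those who had already stayed.

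For relapse the problem is partial. A subject whose relapse ends treatment within 28 weeks of stability is left out, when that relapse should count as an event.

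What is at stake is how two supplementary long-term curves are read. Two programmers could also build different populations from the same sentence.

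**Working it through.** The plan gives no figure for these analyses, so there is nothing to reproduce. The day arithmetic below comes from the documents; every rate is an assumption.

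**Inputs from the documents.** Stability takes at least 12 × 7 = 84 days (SAP 16.1.1.6). The restriction is 28 × 7 = 196 days. Nominal end of treatment in Japan is 52 × 7 = Day 364. The one-day offset in the SAP formulas is ignored. The Week 12 visit window opens at Day 76, but that is short of 12 weeks, so Day 84 is used.

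**Reading 1: achieved treatment, discontinuation.** The last-dose date is both the event date and the end of the qualifying period. The earliest possible event is at 84 + 196 = about Day 280, and 280/364 = 76.9% of follow-up. Before that the curve is fixed at 100%.

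For illustration, let d be true Week 52 discontinuation, s the stability day, and the hazard constant:

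- subset: 1 − (1 − d)^((364 − s − 196)/364)
- all subjects stable at day s: 1 − (1 − d)^((364 − s)/364)

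| Stability day | Subset, d = 20/40/60% | All stable at that day |
|---|---|---|
| 84 | 5.0 / 11.1 / 19.1% | 15.8 / 32.5 / 50.6% |
| 112 | 3.4 / 7.6 / 13.1% | 14.3 / 29.8 / 47.0% |
| 140 | 1.7 / 3.9 / 6.8% | 12.8 / 27.0 / 43.1% |

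In relative terms the gap widens with later stability. The direction does not need a constant hazard. At Day 84, a Weibull shape of 0.5 gives 2.7/6.1/10.7% against 10.9/23.3/37.9%, and a shape of 1.5 gives 7.0/15.3/25.8% against 18.0/36.5/55.7%.

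**Reading 1: relapse.** Let F be true relapse by 28 weeks after stability and p the share of those relapses that end treatment within that time. Assume other discontinuation is independent of relapse. The subset shows (1 − p)F / (1 − pF).

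| F | p = 0 | p = 0.25 | p = 0.5 | p = 1 |
|---|---|---|---|---|
| 10% | 10% | 7.7% | 5.3% | 0% |
| 20% | 20% | 15.8% | 11.1% | 0% |
| 40% | 40% | 33.3% | 25.0% | 0% |

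The documents do not give p. Criterion 5 events always end treatment. Mood-episode hospitalizations do so to the extent that they fall under Protocol 4.4.1.

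**Cross-check by simulation** (200,000 subjects per scenario, exponential times, stability spread over Weeks 12 to 36). Assumed rates were non-relapse discontinuation of 30/45/60% by Week 52, relapse of 15/30/45% by 28 weeks, and 25/50/75% of relapses ending treatment. Across scenarios the achieved-treatment subset showed Week 52 discontinuation of 0.07–0.25, against 0.24–0.66 for all stable subjects. Its first discontinuation was at Week 40.0 every time. A 30% relapse rate showed as about 0.24, 0.18 and 0.10. A subset defined by planned follow-up returned 0.15, 0.30 and 0.45 unchanged.

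**Reading 2: planned follow-up.** Selection on outcome disappears, but two problems remain. Stability at Week 24 leaves nominally 52 − 24 = 28 weeks, which does not exceed 28. By the visit windows it leaves 356 − 176 = 180 to 372 − 160 = 212 days, against 196. And if discontinuation is still counted from Day 1, at least about 12 weeks are event-free, because a subject must stay on treatment to reach stability.

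**The case against.** The strongest reply is that the text does not commit to reading 1. SAP 14.3 defines exposure, which is a different term, while SAP 3.1 uses treatment duration for the planned period. This stands: both readings are open, and most of the size shown above belongs to one of them. The SAP also refers to output templates that are not in the documents, so a definition could sit there.

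Second, a curve for a stated subset describes that subset. It understates discontinuation only if read as describing everyone who reached stability. That is fair, but a discontinuation curve that cannot fall for its first 40 weeks says little even about its own subset.

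Third, Protocol 9.5.3 leaves subgroup details to the SAP. It does, though none of the subgroups it lists is defined by time on treatment, and Protocol 9.1 asks for changes to be listed with reasons. The gap in SAP 3.6 is real but administrative.

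A reader might infer that every early relapse is lost. The documents do not support that: a relapser who stays on study drug is kept and counted, and Protocol 6.2.7 records the number of mood episodes by type during treatment, which suggests that this can happen. A reader might also infer that the study's long-term relapse and retention results are biased. They are not affected by this point, because the unrestricted Japanese Week 52 analyses remain and already keep subjects who stop early.

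**Conclusion.** The concern holds as a minor point about two supplementary, descriptive outputs with an undefined subset. If the subset means achieved treatment, two consequences follow from the documents' own definitions: the discontinuation curve has no possible event before about Day 280 of 364, and later discontinuation among subjects who reached stability is understated. The 5/11/19% against 16/33/51% is only an illustration. It assumes the overall rates, a constant hazard, stability at Day 84 and end at Day 364. The relapse bias lies anywhere from nil to complete, because the share of relapses that end treatment is not given. If the subset means planned follow-up, what remains is an ambiguous cut-off and an unsuitable time origin for discontinuation. No hypothesis depends on either output.

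**What to change.** The simplest change is to delete both restricted analyses. For relapse little is lost, since the unrestricted analysis already starts at stability and censors subjects who leave early.

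If they are kept:

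- Define the subset by planned follow-up in days. For example, take Japanese subjects with a stability date on or before Day 168, so that at least 364 − 168 = 196 planned days remain. State this as at least 28 weeks, which settles the Week 24 boundary.
- Keep these subjects whether or not they later stop treatment.
- Count both endpoints from the stability date, and report the Kaplan-Meier probability at 28 weeks with its 95% confidence interval.
- List the analyses in SAP 3.6 with the reason, including the departure from the Day 1 origin that Protocol 9.5.2 sets for discontinuation.

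The cost is SAP wording and one programmed flag, with no new data. Compared with the achieved-treatment reading, the curves may look less favourable.

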16.1.5. SENSITIVITY ANALYSIS OF EFFICACY VARIABLE(S)

16.1.5.1. Time to Recurrence of a Major Depressive, Manic, Mixed or Hypomanic Episode

Time to recurrence of a DSM-IV-TR major depressive episode will be analyzed using a time-to-event analysis. KM results will be displayed for the 25%, 50% and 75% quartiles, including its 95% confidence interval using the product limit method. The KM figure will be produced to support the analysis.

Likewise, time to recurrence of any DSM-IV-TR manic, mixed or hypomanic episode will also be analyzed in the same way. For determining the above episode types, information will be used from the protocol-defined criteria for meeting a DSM-IV-TR event.

Time to recurrence of DSM-IV-TR major depressive episode, manic, mixed or hypomanic summaries will be presented for all subjects up to Week 28 and repeated for all Japanese subjects up to Week 52 separately.

17. SAFETY OUTCOMES

All output summaries for safety outcomes will be based on the safety population. Listings will include all enrolled subjects.

There will be no statistical comparisons between the treatment groups for safety data, unless otherwise specified with the relevant section.

17.1. ADVERSE EVENTS

Adverse Events (AEs) will be coded using Medical Dictionary for Regulatory Activities (MedDRA) central coding dictionary, Version 19.1. All categories of AEs will be summarized by treatment group for the safety population.

Listings will be provided of TEAEs resulting in death, serious TEAEs, and TEAEs resulting in discontinuation from the study. All three listings will use the safety population.

Treatment-emergent adverse events (TEAEs) are defined relative to Week 28 and Week 52 as follows:

- TEAEs up to Week 28 defined as:

Document:	K:\DSP\SM-13496\RVA97109\Biostatistics\Documentation\SAP	Version Number:	1.0
Author:	[REDACTED]	Version Date:	20MAR2018

Template No: CS_TP_BS016 – Revision 3
Effective Date: 01May2012

Reference: CS_WI_BS005

Copyright © 2012 [REDACTED] All rights reserved.
The contents of this document are confidential and proprietary to [REDACTED]. Unauthorized use, disclosure or reproduction is strictly prohibited.

- o AEs with a start date on or after the date of first dose of study medication through 7 days after last dose of study medication (14 days for serious adverse events and deaths) for subjects outside Japan, or
- o Subjects within Japan who early terminate the study prior to Week 28 will be derived based on the derivation above
- o For subjects within Japan who participate in the study after Week 28, TEAEs will include AEs with a start date on or after the first dose of study medication up to Week 28
- TEAEs up to Week 52 defined as:
 - o AEs with a start date on or after the date of first dose of study medication through 7 days after last dose of study medication (14 days for serious adverse events and deaths) for all subjects within Japan

All AEs with an onset date after the consent date for the long-term study but prior to the first dose in the long-term study will be summarized separately in the long-term study. Adverse events and serious adverse events (SAEs) with completely missing onset dates will be summarized as treatment emergent regardless of severity or relationship to study medication, unless the AE stop date occurs before the date of first dose of study medication.

See Appendix 2 for handling of partial dates for AEs. In the case where it is not possible to define an AE as treatment emergent or not, the AE will be classified by the worst case; i.e. treatment emergent.

An overall summary of subjects within each of the categories described in section 17.1.1 below, will be provided as specified in the templates.

Listings will include TEAEs and Non-TEAEs.

17.1.1. ALL TEAEs

Incidence of TEAEs will be presented by System Organ Class (SOC) and Preferred Term (PT) and also broken down further by maximum severity and relationship to study medication. Summaries will be presented for all subjects up to Week 28 overall and by country, and will be repeated for all Japanese subjects up to Week 52 separately as well.

17.1.1.1. Severity

Severity is classed as 'mild', 'moderate' or 'severe' (increasing severity). TEAEs starting after the first dose of study medication with a missing severity will be classified as 'not specified'. If a subject reports a TEAE more than once within that SOC and PT, the AE with the worst-case severity will be used in the corresponding severity summaries. In determining maximum severity, response values will be ranked in order from minimum severity to maximum severity as values: 'not specified', 'mild', 'moderate', and 'severe'.

An additional summary will be presented for Treatment-Emergent Adverse Events Occurring in at Least 3% of Subjects broken down by maximum severity for all subjects up to Week 28 overall, and will be repeated for all Japanese subjects up to Week 52 by Most Recent or Current Episode.

17.1.1.2. Relationship to Study Medication

Relationship, as indicated by the Investigator, is classed as 'related', 'not related' or 'not specified'. The categories of 'possible', 'probable', and 'definite' will be pooled to create the 'related' category. Similarly, 'not related' and 'unlikely' will be pooled to create the 'not related' designation. If a subject has more than one AE

Document:	K:\DSP\SM-13496\RVA97109\Biostatistics\Documentation\SAP		
Author:	[REDACTED]	Version Number:	1.0
		Version Date:	20MAR2018

Template No: CS_TP_BS016 – Revision 3
Effective Date: 01May2012

Reference: CS_WI_BS005

within an SOC and PT, the subject will be counted once according to the highest relationship. Adverse events with missing relationship will be classified as 'not specified'. In determining highest relationship, response values will be ranked in order from minimum relationship to maximum relationship as values: 'not specified', 'not related', and 'related'.

An additional summary will be presented for Treatment-Emergent Adverse Events Occurring in at Least 3% of Subjects broken down by relationship to study medication for all subjects up to Week 28 overall.

17.1.2. TEAEs LEADING TO DISCONTINUATION OF STUDY MEDICATION

TEAEs leading to permanent discontinuation of study medication will be identified by using the 'action taken' variable collected on the eCRF.

For TEAEs leading to discontinuation of study medication, summaries of incidence rates (frequencies and percentages) by SOC and PT will be prepared. A listing will provide details of these TEAEs and indicate any drug relationship.

